## 7 STUDY INTERVENTION

Intervention families will receive approximately 4 hours of ASL and development specific content related to language and feeding during home visits and phone calls. The initial in-home session with families will focus on teaching ASL signs indicative of hunger, thirst, and satiety. A video and placemat of mealtime signs will be left with families at the completion of the first visit. The remaining sessions, in-

home over the next 3 months and by phone monthly thereafter for 6 months total, will focus on reinforcing ASL signing in addition to focused education on particular aspects of language development (receptive language preceding expressive language and increasing intentional communication), feeding development (such as hunger and fullness cues, fear of new foods, the importance of repeated food exposures, variations in intake from meal-to-meal, and the propensity to reject bitter tastes [many vegetables]), and appropriate portion sizes and variety for healthy growth.

In person visit lesson schedule (monthly from baseline at 4-9 months of age):

Visit 1 (baseline: T1): Signing with infants

Visit 2: Infant communication and responsive feeding

Visit 3: Nutrition, portion sizes, and neophobia

Visit 4 (T2): Infant intentionality

Intervention participants will be contacted by the project manager with 48-hours of in-home study visits (1-4 above) to assess and record whether relevant intervention content was delivered.

## **8 STUDY INTERVENTION ADMINISTRATION**

Randomization will be stratified by age group (for developmental differences; 4-5-months-old, 6-7-months-old, and 8-9-months old). Computerized randomization lists will be generated by study statistician and will be administered by the project manager. Study personnel who code videos of feeding interactions will be blind to group status.

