### **3.2 Allocation to Treatment Groups and Blinding**

Randomization will be stratified by age group (for developmental differences; 4-5-months-old, 6-7-months-old, and 8-9-months old). Computerized randomization lists will be generated by study

statistician and will be administered by the project manager. Study personnel who code videos of feeding interactions will be blind to group status.

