## **4 STUDY PROCEDURES**

**4.1 Screening/Baseline Visit procedures:** Families will be recruited from a community sample through a variety of means, including email listservs, in-person interactions with study personnel, social media posting to local parenting groups, and publicly posted flyers. Those wishing to learn more about the study will contact our project manager, who will conduct screening and enrollment for those wishing to participate in the study.

**4.2 Intervention/Treatment procedures (by visits):** Intervention families will receive approximately 4 hours of ASL and development specific content related to language and feeding during home visits and phone calls. The initial in-home session with families will focus on teaching ASL signs indicative of hunger, thirst, and satiety. A video and placemat of mealtime signs will be left with families at the completion of the first visit. The remaining sessions, in-home over the next 3 months and by phone monthly thereafter for 6 months total, will focus on reinforcing ASL signing in addition to focused education on particular aspects of language development (receptive language preceding expressive language and increasing intentional communication), feeding development (such as hunger and fullness cues, fear of new foods, the importance of repeated food exposures, variations in intake from meal-to-meal, and the propensity to reject bitter tastes [many vegetables]), and appropriate portion sizes and variety for healthy growth.

In person visit lesson schedule (monthly from baseline at 4-9 months of age):

Visit 1 (baseline: T1): Signing with infants

Visit 2: Infant communication and responsive feeding

Visit 3: Nutrition, portion sizes, and neophobia

Visit 4 (T2): Infant intentionality

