where the rest of data collection will take place to minimize participant reactivity. After ASL and knowledge content delivery by the parent educator (experimental group only), participants will then prepare for cardiac data monitoring and video-recording. The initial period of training by the parent educator should allow some time for mother and child to adjust to the presence of study staff in their home and recover from any physiological arousal or reactivity in response to them. Then, an ambulatory electrocardiogram (ECG) monitor will be placed on mother's and infant's chests in order to record RSA patterns throughout the observation. This single channel ECG waveform recorder (Actiwave Cardio; Camntech) will be connected to two disposable ECG electrodes (ConMed Neonatal/Pediatric Huggables) placed below the sternum and on the left side of the body (connected to each other by a short lead). The Actiwave Cardio monitors are flat, lightweight (<8 g), and comfortable with high levels of intra- and inter-instrument reliability as well as good validity of measures. Interbeat interval (IBI) data will be monitored and recorded for R-wave detection (providing an estimate of the degree of vagal influence on heart rate). RA's will instruct mothers on how to place 2 electrodes onto her chest and her infant's chest. After a brief test of the signal strength, the infant's length and weight (in clean dry diaper only) will be measured in triplicate, using a calibrated length board and digital scale. Given the much shorter duration of our proposed monitoring (~1 hour), we feel confident in our ability to capture RSA data in both mother and infant. Then, mothers and infants will be given a 5-minute break to relax in order to give them time for de-escalation after physical measurements. Next, infants will listen to soothing music while seated in a baby seat (or other arrangement recommended by mother; for example, if infant is more comfortable and less likely to become distressed on a blanket or in a crib, we will do this instead) and mothers will read a neutral magazine (gardening) for a 4-min baseline measurement. Monitors will be worn for the entirety of the visit and feeding events will be marked within the time-stamped data. Video-recording will begin after intervention (or usual care) delivery, with mothers asked to wait at least 10 minutes after the video-recording begins before feeding their child. They can then feed their child whenever they feel it is appropriate. One camera will focus on the mother's facial expressions and movements and the second camera will focus on the infant's facial expressions and movements. As long as the infant is stationary during feeding (in mother's lap, a highchair, or booster seat), the infant's videographer will focus the camera at the beginning of the recording and then step away from the camera to minimize intrusiveness. Both videographers will swivel the camera and use the digital zoom to follow mother or child throughout the observation. From this position, the videographers can use the digital viewfinder and be out of view from the feeding room if possible. Video-recording will last until 2 minutes after the child's last bite of food. We are currently testing and refining these data collection protocols. All other self-report data from questionnaires other than NDSR will be entered in the field using Research Electronic Data Capture (REDCap) through UNC-Chapel Hill CTSA. Within a week of T1, T2, and T3, two 24-hour recalls (to account for day-to-day variation) will be collected using NDS-R software by telephone five to 10 days apart. Twenty-four-hour recalls provide intake during a specified period, are open-ended, can accommodate various foods or food combinations, do not require literacy and have a relatively low respondent burden.

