Those wishing to learn more about the study will contact our project manager, who will conduct screening and initial enrollment for those wishing to participate in the study. Screening and initial enrollment occurs by telephone. Any contact information for individuals who decline to participate or are not eligible is immediately deleted from the contact database.

Potential subjects will be contacted through their preferred method, telephone or email. An initial email from the project manager, research assistant, or PI will include a question about whether our research team can leave a voicemail with a request for call back. If potential subjects choose to call rather than email and they are put through to voicemail, the voicemail will instruct them to answer the question about whether our research team can leave a voicemail with a request for call back. Contact information will be entered into a password protected contact database.

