## **12 CONSENT PROCESS**

Subjects will be contacted by telephone prior to the home visit for data collection. During the telephone conversation, the study will be described and telephone consent to participate will be obtained. Once in the family home, the study will be described once more and written consent will be obtained.

We have put together a combined Adult Consent and Parental Permission form. Parents will be given the form for review on-site and study staff will go through the permission form verbally with the parent(s)

and offer to answer any questions prior to parental signature. If mothers of infants are adolescents, we will obtain their permission for their infant to participate, their assent to participate, and their parent or legal guardian's permission for them (the adolescent parent) to participate. We will have Spanish language versions of the Combined Adult Consent and Parental Permission forms for review in Spanish-speaking participants' homes. A bilingual research staff member on site will provide oral interpretation as needed.

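### The project manager who screens and enrols families also administers the randomisation lists, and the plan describes no allocation concealment and no time of randomisation

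*Combined protocol and SAP*

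**What the plan says.** On allocation, Section 8 states: "Computerized randomization lists will be generated by study statistician and will be administered by the project manager". Section 3.2 repeats this. Both sections stratify by three infant age bands and blind the video coders. Neither gives a block scheme, a means of concealment or a time of randomisation.

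On entry to the study, Section 4.1 says interested families contact "our project manager, who will conduct screening and enrollment for those wishing to participate in the study". Section 11 gives the same role "will contact our project manager, who will conduct screening and initial enrollment for those wishing to participate in the study", and adds: "Screening and initial enrollment occurs by telephone".

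On consent, Section 12 has consent by telephone before the visit. Then: "Once in the family home, the study will be described once more and written consent will be obtained".

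On the order of the home visit, Section 10 says: "After ASL and knowledge content delivery by the parent educator (experimental group only), participants will then prepare for cardiac data monitoring and video-recording". Sections 4.2 and 7 make the first lesson part of the T1 visit.

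**The concern.** The person who decides whether a family enters should not be able to know which arm the next family will get. Here one role does the telephone screening and initial enrolment and also controls the lists, and no safeguard separates the two tasks.

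Foreknowledge need not involve misconduct. It can act through how firmly a family is encouraged, how soon the visit is booked, or how a borderline criterion is read. Section 3.4 leaves some room for judgement, for example on what counts as regular daycare, on whether a delay makes eating or communicating difficult, and on willingness to learn the signs. Section 5 also names the project manager as the source of the screening and enrolment logs, so a later check would rest on the same person's records.

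At stake is the comparability of the arms. Intention-to-treat (Section 6.3) keeps dyads in the arm they were given, but does not help if entry itself depended on the arm. Covariates adjust only for what was measured.

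**Working it through.** **The roles side by side**

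| Step | Who, when | Where |
|---|---|---|
| Generate lists | Study statistician | Sections 3.2, 8 |
| Administer lists | Project manager | Sections 3.2, 8 |
| Screening, initial enrolment | Project manager, by telephone | Sections 4.1, 11 |
| Written consent | Study staff, in the home | Section 12 |
| First lesson (intervention arm only) | Parent educator, before ECG, weight, length and video | Section 10 |
| Moment of randomisation | Not stated | – |
| Concealment method | Not stated | – |

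In the intervention arm the assignment must be known before the lesson, and so before the T1 measurements that follow it. Whether it is known before written consent is not stated.

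**How large could the bias be?** The documents give no steering rate, so this is an illustration.

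Inputs from Section 6.4: AR(1) correlation with rho = 0.9, 32 dyads per group (40 × 0.8), one-sided 0.05, target 0.4 SD by T3.

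*The plan's own figure first.* Section 6.4 claims power above .86. A generalised least squares test with a common baseline mean and differences of 0, 0.2 and 0.4 SD gives a squared noncentrality of (32/2) × [0.2² × 1.81 + 0.4² − 2 × 0.9 × 0.2 × 0.4]/0.19 = 16 × 0.4653 = 7.444. Power is Φ(√7.444 − 1.645) = Φ(1.083) = 0.861, which matches. The plain T3 − T1 contrast gives 0.829. Power is not in dispute here.

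*Standard error of the slope contrast.* The slope model in Section 6.3 has a free group term. With three equally spaced visits, its group-by-time test is then the T3 − T1 contrast.
- The T1–T3 correlation is 0.9² = 0.81.
- The variance of change is 2(1 − 0.81) = 0.38, so the SD of change is √0.38 = 0.616 outcome SD.
- SE = √(2 × 0.38/32) = 0.154 SD.

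*Error rate with no true effect.* It is Φ(bias/0.154 − 1.645). Assume 10% of dyads are steered, so bias = 0.10 × the difference in steered dyads.

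| Steered dyads differ by | Bias in slope contrast (SD) | One-sided error |
|---|---|---|
| 1 SD in level, stable over time | 0 | 5% |
| 1 SD in baseline level, regressing under AR(1): 0.1 × (1 − 0.81) | ±0.019 | 3.9% or 6.4%, by direction |
| 1 SD of change (0.616 outcome SD) | 0.062 | Φ(−1.245) = 11% |
| 1 outcome SD in change | 0.100 | Φ(−0.996) = 16% |

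The last two rows assume steering that favours the intervention. In the opposite direction the error falls below 5% and a true effect would be masked.

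*The alternative model.* Section 6.3 also allows testing group differences at each visit. For T3 means, SE = √(2/32) = 0.25. A stable level bias of 0.10 SD then does not cancel, and the error is Φ(0.10/0.25 − 1.645) = 11%.

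**The case against.** **The documents do not say the lists are visible.** A reader might infer that allocation is known to be unconcealed. The text says only that the project manager administers the lists. That could mean an open sheet, sequential envelopes or a locked system. This stands. What can be said is that no concealment is described and that the enroller controls the lists.

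**Other staff share the work.** Section 11 has an onsite recruiter in clinics and lets a research assistant or the investigator send the first email. Section 12 has study staff take consent at home. Many criteria, such as language, prematurity and age, are factual. This narrows the room for steering, but does not separate list access from screening and enrolment. Encouragement and scheduling stay open.

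**Assignment need not precede written consent.** A reader might infer that it must, because the lesson comes early in the T1 visit. That does not follow. Families consent by telephone beforehand, and the assignment could be released in the home between signature and lesson.

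**The slope model absorbs some of the bias.** This is correct for a stable difference in level, as the working shows. It fails for differences in trajectory or for unmeasured prognosis. The visit-by-visit model is more exposed.

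**It is a Stage 1 developmental study.** True, but it names a growth outcome as primary, plans formal tests and will use its effect sizes to plan later studies (Sections 2.1 and 6.3). Biased estimates would carry forward.

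**Conclusion.** The point holds. It rests on a stated assignment of roles together with the absence of any described concealment or time of randomisation. It does not rest on evidence that anyone will see or misuse upcoming assignments.

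The size of the bias cannot be known from the documents. If 10% of dyads are steered, the one-sided error of the slope test is about 4–6% when they differ by 1 SD in baseline level only. It is about 11–16% when they differ in change by 0.6–1 outcome SD in the intervention's favour. The 16% should not be read as the expected error: it needs a difference of 1/0.616 = 1.6 SDs of the change distribution. The case for acting does not depend on any of these figures. Selection at entry cannot be fully undone in the analysis, and preventing it is cheap.

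**What to change.** In Sections 3.2 and 8, replace administration by the project manager with one of two arrangements:

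- the statistician holds the list and releases each assignment on request; or
- the list is loaded in a locked module. REDCap is already used for data capture (Section 10), but the plan does not say whether its randomisation module is available.

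In either case, enrolling staff have no list access, and the size of any blocks is not disclosed to them. Each assignment is released only after eligibility and consent are recorded. This can be done in the home, after written consent and before the first lesson, so the present visit order is kept. State that time in the plan.

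The cost is set-up work and an on-site release step at the T1 visit, where the parent educator must be ready for either arm.

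Releasing the assignment after the T1 measurements is optional. It would also keep baseline data free of the lesson, but it reverses the visit order in Section 10, where the training period is meant to let the dyad settle before recording. That would be a change to visit procedures, not only to the wording of Sections 3.2 and 8.

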## **9 SAFETY MANAGEMENT**

Study visit confirmation will occur prior to study visits and assessment of self-reported health of parent and infant will be conducted prior to data collection. Study personnel will be on-site in subjects' homes for the duration of data collection and will monitor the response of subjects during data collection. Should any concerns arise during data collection, they will be addressed immediately by study personnel and the PI and Co-I will be notified as soon as possible if they are not on site. Though unlikely, should any concerns arise after data collection, subjects will be given the PI's contact information to share their concerns and the PI will address concerns directly or through appropriate referrals. Any concerns that arise over the course of the study will be recorded and aggregated as part of the feasibility data and shared with the research team and the IRB as necessary.

We do not anticipate that any questions, anthropometric measurements, observations, or collection of cardiac data will cause discomfort or embarrassment, but mothers may stop interviews at any time, tell us that they do not wish to answer a question, refuse to allow infant measurement, stop an observation, or refuse collection of cardiac data at any time. We will respect their wishes. We will also let parents/primary caregivers know the following: "In addition, there may be uncommon or previously unknown risks that might occur. You should report any problems to the researchers. We are mandated to report any instances of child abuse."

Thus, individual subjects may electively withdraw from the study or the PI may withdraw an individual subject, or in this case mother-infant dyad, if they fail or are unable to comply with study procedures.

## **10 DATA COLLECTION AND MANAGMENT**

Home visits will be scheduled to start about 45 minutes before a normal feeding time. Mothers will provide all food and will be encouraged to feed their children a typical meal. Upon arrival, four tripod-mounted digital video cameras will be set up; two in the typical place the baby is fed and two in the room

where the rest of data collection will take place to minimize participant reactivity. After ASL and knowledge content delivery by the parent educator (experimental group only), participants will then prepare for cardiac data monitoring and video-recording. The initial period of training by the parent educator should allow some time for mother and child to adjust to the presence of study staff in their home and recover from any physiological arousal or reactivity in response to them. Then, an ambulatory electrocardiogram (ECG) monitor will be placed on mother's and infant's chests in order to record RSA patterns throughout the observation. This single channel ECG waveform recorder (Actiwave Cardio; Camntech) will be connected to two disposable ECG electrodes (ConMed Neonatal/Pediatric Huggables) placed below the sternum and on the left side of the body (connected to each other by a short lead). The Actiwave Cardio monitors are flat, lightweight (<8 g), and comfortable with high levels of intra- and inter-instrument reliability as well as good validity of measures. Interbeat interval (IBI) data will be monitored and recorded for R-wave detection (providing an estimate of the degree of vagal influence on heart rate). RA's will instruct mothers on how to place 2 electrodes onto her chest and her infant's chest. After a brief test of the signal strength, the infant's length and weight (in clean dry diaper only) will be measured in triplicate, using a calibrated length board and digital scale. Given the much shorter duration of our proposed monitoring (~1 hour), we feel confident in our ability to capture RSA data in both mother and infant. Then, mothers and infants will be given a 5-minute break to relax in order to give them time for de-escalation after physical measurements. Next, infants will listen to soothing music while seated in a baby seat (or other arrangement recommended by mother; for example, if infant is more comfortable and less likely to become distressed on a blanket or in a crib, we will do this instead) and mothers will read a neutral magazine (gardening) for a 4-min baseline measurement. Monitors will be worn for the entirety of the visit and feeding events will be marked within the time-stamped data. Video-recording will begin after intervention (or usual care) delivery, with mothers asked to wait at least 10 minutes after the video-recording begins before feeding their child. They can then feed their child whenever they feel it is appropriate. One camera will focus on the mother's facial expressions and movements and the second camera will focus on the infant's facial expressions and movements. As long as the infant is stationary during feeding (in mother's lap, a highchair, or booster seat), the infant's videographer will focus the camera at the beginning of the recording and then step away from the camera to minimize intrusiveness. Both videographers will swivel the camera and use the digital zoom to follow mother or child throughout the observation. From this position, the videographers can use the digital viewfinder and be out of view from the feeding room if possible. Video-recording will last until 2 minutes after the child's last bite of food. We are currently testing and refining these data collection protocols. All other self-report data from questionnaires other than NDSR will be entered in the field using Research Electronic Data Capture (REDCap) through UNC-Chapel Hill CTSA. Within a week of T1, T2, and T3, two 24-hour recalls (to account for day-to-day variation) will be collected using NDS-R software by telephone five to 10 days apart. Twenty-four-hour recalls provide intake during a specified period, are open-ended, can accommodate various foods or food combinations, do not require literacy and have a relatively low respondent burden.

In order to protect against breach of confidentiality, access to relevant data will be restricted to research team members for the proposed study. All data other than the videos will be accessible only through a password-protected database (REDCap). Video and cardiac data will be downloaded from their respective collection devices and transmitted via secure authentication through the UNC ITS Research Computing Secure FTP Server. Video and cardiac data will then be downloaded onto encrypted and password protected external hard drives that will be housed in one locked room within the Observational Suite of the Biobehavioral Laboratory in the UNC School of Nursing. Research assistants involved in data collection will notify the PI and Co-I when new data is available for review in the Biobehavioral Laboratory. [name] will supervise access to the videos by the two research assistants involved in video coding.

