## **3 INVESTIGATIONAL PLAN**

### **3.1 Study Design**

Two-group randomized repeated measures design with an intervention group and a control group of mother-infant dyads. For the intervention, we plan to teach mothers American Sign Language (ASL) signs indicative of hunger, thirst, and satiety, which they will in turn teach their preverbal infant. This training in ASL will be augmented with targeted information for mothers about infants' capacities to self-regulate energy intake in response to hunger and satiety and communicate those states with intention. Mothers also will be taught about expected development of infants' eating behaviors and nutritional requirements to support healthy growth. For the control group, dyads will participate in the same data collection as the intervention group and engage in their usual care provided by their health care provider, but they will not receive intervention content unless they elect to receive written lesson content once the study's data collection has ended and they have been debriefed.

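### At T1 and T2, but not T3, only the experimental arm has a lesson before the filmed meal, so settling time and meal timing can differ by arm in the change analyses of feeding responsiveness

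*Combined protocol and SAP*

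**What the plan says.** Section 10 sets the start of every data-collection visit relative to the infant's routine: "Home visits will be scheduled to start about 45 minutes before a normal feeding time". It makes no allowance for arm or visit.

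The order of events then differs by arm: "After ASL and knowledge content delivery by the parent educator (experimental group only), participants will then prepare for cardiac data monitoring and video-recording". Section 10 gives the lesson a second function, as time to get used to staff and recover from arousal at their arrival: "The initial period of training by the parent educator should allow some time for mother and child to adjust".

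Both arms then have electrode placement, triplicate length and weight, a 5-minute break, a 4-minute resting baseline, and at least 10 minutes of video before feeding. After that the mother feeds when she judges it right.

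On the amount of content, Section 4.2 says: "Intervention families will receive approximately 4 hours of ASL and development specific content related to language and feeding during home visits and phone calls". The split between visits and calls is not given. Delivery is "in-home over the next 3 months and by phone monthly thereafter for 6 months total", and the in-person schedule includes "Visit 1 (baseline: T1): Signing with infants" and "Visit 4 (T2): Infant intentionality". No in-home lesson is listed for the 6-month visit (T3).

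For controls, Section 3.1 says "they will not receive intervention content unless they elect to receive written lesson content" after data collection has ended, and that usual care comes from the family's own provider.

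**The concern.** The conditions under which the meal is observed differ by arm at T1 and T2 and become the same at T3. This would be so even if the lesson taught nothing. Experimental dyads have had a period with staff in the home before measurement begins, and their meal may start later relative to the infant's usual time.

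The RCFCS rates responses to hunger and fullness cues, and RSA change is taken from a resting recording. Both could plausibly depend on how hungry and how settled the infant is. A difference in conditions that is present at T1 and T2 and absent at T3 has the shape of a group-by-time effect, which is what the slope model in Section 6.3 tests. Blinding the video coders does not help, because the infant's actual state would differ.

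At stake are the change analyses for tertiary outcome A, the T2 effect sizes meant for planning later studies, and the exploratory analysis relating responsiveness to RSA.

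**Working it through.** The plan gives no figure for meal timing, so there is none to reproduce. The check is a timeline.

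**Inputs from the documents.** Lead time before the usual feed: 45 min. Content: about 4 h = 240 min. Home lessons: 4. Break 5 min, baseline 4 min, wait at least 10 min.

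**Assumptions.**
- Content is spread evenly over 4, 6 or 7 contacts (four visits plus 0, 2 or 3 calls).
- Preparation (cameras, electrodes, signal test, length and weight) takes 10-25 min.
- The 10-min wait either overlaps the break and baseline (10 min in total) or follows them (5 + 4 + 10 = 19 min).

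**Lesson length.** 240/4 = 60 min; 240/6 = 40 min; 240/7 = 34 min.

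**Earliest feed after arrival = lesson + preparation + fixed waits.**

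| | Shortest | Longest |
|---|---|---|
| Control | 10 + 10 = 20 min | 25 + 19 = 44 min |
| Control, relative to usual feed | 20 - 45 = 25 min before | 44 - 45 = 1 min before |
| Experimental, T1 and T2 | 34 + 10 + 10 = 54 min | 60 + 25 + 19 = 104 min |
| Experimental, relative to usual feed | 54 - 45 = 9 min after | 104 - 45 = 59 min after |

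In the limiting case of no preparation time, overlapping waits and a 34-min lesson, the experimental feed is possible at 44 min, just on time.

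**Gap between arms.** If every mother feeds as early as allowed, the gap equals the lesson length, 34-60 min, whatever the preparation time. If control mothers wait for the usual feeding time, it narrows to the overrun, 9-59 min. At T3, with no lesson, it is 0.

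**Route into the analysis.** With visits at 0, 3 and 6 months, the linear slope is essentially (T3 - T1)/6 per month, and T2 carries almost no weight. A shift of b in the experimental arm at T1 and T2 but not T3 moves the T3 - T1 contrast by b in the opposite direction.

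**Illustration (b is assumed; the documents give no value).** Section 6.4 has 32 dyads per arm, AR(1) with parameter 0.9, and one-sided alpha 0.05. The T1-T3 correlation is 0.9² = 0.81, so the SD of change is √(2(1 - 0.81)) = 0.616 and the standard error is 0.616 × √(2/32) = 0.154. Power for 0.4 SD is then 0.83. Adjusting for T1 instead gives 0.861, in line with the stated figure, so the power statement is not in dispute here.

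| Assumed b (SD) | One-sided type I error if T1/T2 scores are lowered | Power for a true 0.4 SD if they are raised |
|---|---|---|
| 0 | 0.05 | 0.83 |
| 0.1 | 0.16 | 0.62 |
| 0.2 | 0.36 | 0.36 |
| 0.3 | 0.62 | 0.16 |

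**The case against.** The strongest reply is that the T3 comparison is clean. Section 6.1 makes T3 the primary endpoint, tertiary A(2) is framed as a difference by T3, and the alternative model in Section 6.3 tests the arms at each timepoint. With no lesson at T3, that contrast is unaffected. This stands, and it limits the problem to the slope test, within-arm change (tertiary A(1)) and the T2 results.

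A reader might infer that the experimental meal is known to fall well past the usual time. The documents do not show that. Lesson length is not given, the overrun starts at about 9 minutes under the stated assumptions, and the limiting case is on time. These are also earliest feeds, not actual ones, because mothers choose when to feed.

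A reader might also infer that controls have no chance to settle. Both arms have camera set-up, the break, the baseline and the wait, and at T1 the consent discussion (Section 12). Only the initial period that Section 10 relies on is missing for controls, and the break is meant for recovery from the physical measurements. Section 10 does mention usual-care delivery before recording, but it describes no such activity, and Section 3.1 places usual care with the family's own provider.

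Finally, one might read this as bias in a between-arm RSA test. None is planned: RSA is an exploratory concordance objective, outside the outcomes listed for the group models. What remains there is a possible shared influence on responsiveness and RSA, and distorted by-group descriptives and effect sizes.

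**Conclusion.** The concern holds in a limited form. Followed as written, Section 10 together with the lesson schedule creates a difference in measurement conditions between arms at T1 and T2 that is not present at T3. On the stated assumptions about lesson and preparation time, the earliest experimental feed is about 9-59 minutes after the usual time, while controls can feed at or before it. The T3 part rests on the lesson schedule in Sections 4.2 and 7, since Section 10 describes one sequence without separating visits.

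A difference in hunger or arousal is plausible but not demonstrated, and its direction and size are unknown. The error rates above show how sensitive the slope test would be; they do not estimate an actual bias. The T3 between-arm contrast, weight-for-length and the telephone dietary recalls are little affected. Because the exposed outcomes are tertiary and exploratory, this is a cheap improvement worth making, not a flaw in the primary analysis. Section 10 says its collection procedures are still being refined, so the change can be made there.

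**What to change.** In Section 10, anchor the measurement sequence, not staff arrival, to the feed. Electrode placement would begin at one fixed interval before the usual feeding time in both arms at T1, T2 and T3, with staff arriving earlier by the lesson length where a lesson comes first. Give both arms the same short neutral settling period before electrodes at all three visits. Experimental dyads would still spend longer with staff at lesson visits, but meal timing would match and both arms would have a defined settling period.

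Alternatively, deliver the lesson after the observation. The lesson-driven difference is then 0, and on the same assumptions both arms could feed 20-44 minutes after arrival, within the 45-minute lead. With this order the settling period is optional as far as the arm difference is concerned.

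Under either option, record the time of last feed; feeding events are already time-stamped. Use time since last feed only in a sensitivity analysis. It is measured after randomisation, and an intervention about hunger and fullness cues may itself change it, so adjusting for it in the main model could remove part of a real effect.

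The cost is earlier arrival at lesson visits under the first option, somewhat longer visits in both arms where the settling period is added, one data field and a wording change.
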